Project title:

Effects of in situ simulation-based team training on clinical performance during pediatric cardiac arrest: An intervention study comparing two Danish Regions.

2024/06/18

BACKGROUND AND AIMS

Treating critically ill newborns and children is a challenge in pediatric departments [1]. The rare encounter with critically ill pediatric patients results in limited experience and a lack of routine for each healthcare professional (HP)[2]. Numerous studies document that emergency treatment of pediatric and neonatal patients often fails to meet standard guidelines for treatment [3][4][5][6]. A sentinel event alert from 2004 showed that ineffective communication played a role in nearly three-quarters of neonatal deaths or permanent disabilities [7]. Furthermore, a recent study identified a lack of training in pediatric resuscitation skills in Danish hospitals [8]. Accordingly, these factors are major issues challenging the treatment provided for pediatric in-hospital cardiac arrest (pIHCA).

Outcome and survival in critical situations depend on how HPs use technical skills and teamwork competencies [9][10][11]. Simulation-based team training (SBTT) is a well-known and effective method to improve team performance in high-stake and time-sensitive situations, without putting actual patients at risk [12][13]. SBTT develops leadership, teamwork, and communication, and mastering such teamwork competencies is shown to improve outcomes and survival in critical situations [14][15][16]. However, retention of achieved competencies is a major challenge, but recent observational studies demonstrated improved technical pediatric basic life support skills after short simulation sessions with a high frequency of repeat [17][18]. The HPs in these studies are however limited to selected groups and tests are performed exclusively on skill stations. Further, a recent review of optimal simulation training methods concludes that more high-quality research comparing training effectiveness is needed [19].

We therefore aim to investigate the effects of a novel high-frequency training program on teamwork, team effectiveness, and treatment quality during in-situ simulated pediatric in-hospital cardiac arrest. In the intervention group, healthcare professionals will conduct high-frequency simulation-based team training (four training sessions in one year, approx. three months apart). The control group will conduct simulation-based team training ‘as usual’ at a two to three times lower frequency (based on unpublished data).

We hypothesize that high-frequency training will affect primary outcomes as specified: 1) Improve teamwork competences, 2) Reduce time (seconds) to recognition of cardiac arrest, 3) Reduce time (seconds) to initiation of cardiopulmonary resuscitation, 4) Reduce longest chest compression pause duration.

MATERIALS AND METHODS

DESIGN. We will conduct a non-randomized controlled intervention study in two comparable Danish Regions. Both regions include a university hospital and three regional hospitals and each region serves approximately 1.200.000 inhabitants. We aim to include all HPs handling acute patients from the pediatric departments in both regions (approx. 600 employees in each region).

INTERVENTION. Participants in the intervention Region will from April 1st, 2023 to April 1st, 2024, be exposed to a high-frequency training program, in which each HP will attend four SBTT sessions in one year, approx. three months apart. Three-month intervals were chosen based on knowledge of retention of technical skills [17][18]. Sessions are estimated to last 30 to 120 minutes. A local investigator in each pediatric department will be responsible for planning the SBTT sessions. The sessions consist of cases from the abovementioned “scenario bank” including debriefing and will be facilitated by a local certified simulation facilitator.

Pediatric departments in the control Region will conduct SBTT “as usual” with no implemented simulation program and with a 2.5 times lower frequency (based on unpublished data). The simulation activity in both groups will be meticulously registered in a secure electronic database. Each HP has an individual “log” that is registered immediately after each training by a local investigator. Registration began on January 1st, 2023, and terminated on March 31st, 2024.

The intervention is supported by four preliminary initiatives:

- 1) 15 extra pediatric simulation facilitators were educated, bringing the total number up to 40.
- 2) A two-day pre-intervention workshop for all pediatric simulation facilitators.
- 3) A “scenario bank” containing standardized scenarios on common pediatric and neonatal emergencies was created and made accessible for simulation facilitators to support consistency in the intervention.
- 4) Purchase of equipment. Eight Laerdal manikins. Four SimPads. Four monitors. During the intervention year, these will rotate between the pediatric departments.

DATA COLLECTION. To get the most realistic clinical performance assessment, we will conduct unannounced in-situ simulations of pIHCA before and after the intervention in all hospitals. These simulations will be video-recorded and are distinctly different from the high-frequency training program described in the intervention. The dates of the simulations are unknown to everyone except the head nurse who will assign a patient room for the simulation and the researchers enter the room unseen. An advanced manikin (Laerdal Little Baby Q-CPR) is placed in a hospital bed. A nurse is called to the room and presented with a case story whereafter the simulation session begins. Before

the study period, all staff members received information informing them to act exactly as they would in a real emergency with a true patient (call routines, equipment, medicine, etc.). Four GoPro cameras are placed for recording audio and footage to enable assessment. Two assessors will independently evaluate each video in a random order (blinded to pre/post and intervention/control) to score and extract data. At least one assessor of each video recording will be recruited from outside the participating regions to ensure blinding related to recognizability. Discrepancy between observers will be settled by discussion and by including a third rater if needed.

[figure not shown]

Figure 1. Overview of study design.

A total of 122 unannounced simulations will be conducted for performance assessment. Pre-intervention simulations count 32 in the intervention region and 10 in the control region (a lower number to avoid training and Hawthorne effects)[20]. Post-intervention simulations are expected to be 40 in each region.

PRIMARY OUTCOMES.

- 1) Teamwork competencies. Global team score, assessed with “Team Emergency Assessment Measure” measuring leadership control, communication, cooperation, coordination, team climate, adaptability, situation awareness, prioritization, and clinical standards [21][22][23][24].
- 2) Time (seconds) until cardiac arrest is recognized.

- 3) Time (seconds) to initiation of cardiopulmonary resuscitation within standard guidelines for neonates/children.
- 4) Longest chest compression pause duration.

SECONDARY OUTCOMES.

- 1) Time (seconds) to: call for help, arrival of defibrillator and first rhythm check.
- 2) Proportion of compressions and ventilations within recommendations for depth/rate and tidal volumes, respectively.

STATISTICS. Parametric data will be reported as mean (\pm standard deviation (SD)) and non-parametric data as median (1st quartile; 3rd quartile). Data will be analyzed using appropriate parametric and non-parametric tests. A two-sided p-value < 0.05 will be considered statistically significant. We will fit Linear regression models to adjust for important covariates. Primary analyses will compare pre- and post-intervention data between intervention and control regions. Secondary analyses will compare post-intervention outcome measures for each sub-study by the team members' training exposure in the preceding year regardless of intervention/control status; including the number, timing, and topic of training sessions.

Sample size considerations: For sub-study 1, a total of 62 recordings would be needed to show an improvement in the overall TEAM score of 5 points with a power of 80% and a standard deviation of 7 points. For sub-study 2, a total of 62 recordings would be needed to show an improvement in time to detection of cardiac arrest of 10 seconds with a power of 80% and a standard deviation of 14. For sub-study 3, a total of 64 recordings would be needed to show an improvement of 30% in the longest chest compression pause duration with a power of 80%.

RESEARCH PLAN AND FEASIBILITY

The preliminary initiatives and the intervention have been completed as part of a related project (Fellow PhD, [name]). Future PhD student, [name], has successfully conducted the collection of the pre-intervention video recordings and is currently conducting the post-intervention video recordings, which are proceeding according to plan with an expected total of 120 videos of SBTT from both regions. The project group has the necessary clinical network and academic competencies to analyze these highly interesting data with expectations of at least three academic articles and presentation of these at both national and international conferences. The feasibility of this Ph.D. project is unarguably good, and it will add novel and invaluable clinical data to an existing data collection.

ETHICS

The studies comply with the recommendations from the Danish Central Ethics Committee. All participants will give their written consent. Data will be handled according to The Danish Data Protection Agency and the European Union Act on protecting personal data. The project has been reported to the internal registry of research projects, the Central Denmark Region, and the Danish National Committee on Research Ethics.

PERSPECTIVES

By providing important knowledge on optimizing and implementing large-scale high-frequency training strategies, this project is expected to improve the quality of treatment of pIHCA, with an anticipated improvement in mortality and morbidity among survivors. We believe psychological safety among HPs will increase, hopefully with decreased sick leave and employee turnover as a positive side effect. We expect the results to influence the planning and implementation of future onboarding and refresher training programs to ensure high value-for-money approaches in a challenged healthcare system.

REFERENCES

- 1 <https://http://www.erc.edu> ERCEPALSE. 2021.
- 2 Carlsson M. National Behandlingsvejledning for Kritisk Syge Børn. *DasaimDk* 2014;:1–107.
- 4 Root L, van Zanten HA, den Boer MC, *et al.* Improving Guideline Compliance and Documentation Through Auditing Neonatal Resuscitation. *Front Pediatr* 2019;**7**:294. doi:10.3389/fped.2019.00294

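### Both video assessors are said to be blinded to intervention/control, but the safeguard against recognition covers only one of them, and consensus by discussion can carry the other's knowledge into the TEAM score

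*Protocol*

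**What the plan says.** All the scoring rules stand together in the protocol, Materials and Methods, DATA COLLECTION.

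- Blinding is stated for both assessors, without exception: "Two assessors will independently evaluate each video in a random order (blinded to pre/post and intervention/control) to score and extract data".
- The safeguard against recognition follows: "At least one assessor of each video recording will be recruited from outside the participating regions to ensure blinding related to recognizability".
- Disagreement is handled thus: "Discrepancy between observers will be settled by discussion and by including a third rater if needed". Where the third rater comes from is not stated.
- The scored material has picture and sound: "Four GoPro cameras are placed for recording audio and footage to enable assessment". It is filmed in situ, in patient rooms of the participating hospitals.

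Under DESIGN, allocation is by region and not randomized: "Both regions include a university hospital and three regional hospitals", with roughly 600 employees each. Under INTERVENTION, one region has four sessions a year and the other trains as usual, "with no implemented simulation program and with a 2.5 times lower frequency (based on unpublished data").

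Under STATISTICS, the main comparison is: "Primary analyses will compare pre- and post-intervention data between intervention and control regions". The next is: "Secondary analyses will compare post-intervention outcome measures for each sub-study by the team" members' training over the past year, whichever arm they belong to.

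**The concern.** The protocol treats recognition as a threat to blinding, yet requires protection for only one of the two people who score each video. Because arm and region are the same thing, an assessor who recognises a colleague, a voice or a ward knows the arm. No other measure against recognition is stated. The first scores are independent, but any discrepancy goes to discussion, and there an assessor who knows the arm can influence the agreed value.

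The exposure is greatest for the global TEAM score, which rates matters of judgement such as leadership, communication and team climate. Time to recognition of the arrest also needs some judgement, though less. The other timed outcomes are closer to clock readings.

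At stake is a regional preference in the ratings that could be read as an effect of training.

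**Working it through.** **Side by side.** Blinding to arm is claimed for two assessors of two; the outside-region rule guarantees it for one of two; the consensus rule uses both. The claim is therefore wider than the safeguard. This follows from the text alone. The arithmetic below only gives a sense of size.

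**The plan's own scale.** Under STATISTICS the TEAM score is planned for a 5-point improvement, SD 7, power 80%, two-sided 0.05.
- n per group = 2 × (1.960 + 0.842)² × (7/5)² = 30.8, so 31, or 62 in total. This reproduces the stated 62. It is used here only to fix the scale (5 points, SD 7).

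**Assumptions, none of them in the protocol.**
- p = 0.25: an in-region assessor recognises only videos from their own hospital, one of four in the region, with videos spread evenly.
- b = 1 to 3 TEAM points: the shift in that assessor's score on recognised videos.
- Consensus lands midway between the two assessors.
- Only one region's videos are affected, and recordings are independent.

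**Step 1: shift in one region's mean** = p × b / 2.
- b = 1: 0.25 × 1 / 2 = 0.125 points, 2.5% of the 5-point target.
- b = 2: 0.25 points, 5%.
- b = 3: 0.375 points, 7.5%.

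**Step 2: pre/post-by-region contrast** (32 and 10 recordings before, 40 and 40 after).
- SE = 7 × √(1/32 + 1/10 + 1/40 + 1/40) = 2.98.
- Shift the same before and after: it subtracts out, so the bias is 0.
- Shift only in the post-intervention videos: bias 0.125 to 0.375 points, at most 0.375 / 2.98 = 0.13 SE.

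**Step 3: plain post-intervention comparison of regions** (40 v 40).
- SE = 7 × √(2/40) = 1.57. Nothing cancels, so the bias is 0.125 to 0.375 points, at most 0.24 SE.

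**Step 4: planned post-intervention analysis by exposure**, taken as linear in number of sessions and without region in the model.
- Mean exposure is 4 sessions in the intervention region and 4 / 2.5 = 1.6 in the control region, so D = 2.4.
- Let s be the within-region SD of exposure (assumed). With equal numbers per region, the share of a regional shift carried into a D-session contrast is (D²/4) / (D²/4 + s²).
- s = 0.5: 1.44 / 1.69 = 0.85, giving 0.107 to 0.320 points.
- s = 1: 1.44 / 2.44 = 0.59, giving 0.074 to 0.221 points.
- The protocol's aims give the control frequency as two to three times lower. Then D = 2.0 to 2.67, and the share is 0.80 to 0.88 (s = 0.5) or 0.50 to 0.64 (s = 1).
- SE of the 2.4-session contrast at s = 0.5: 2.4 × 7 / √(80 × 1.69) = 1.45. The largest bias is 0.32 / 1.45 = 0.22 SE, which moves a 5% two-sided false-positive rate to about 5.6%.
- At s = 1: SE = 2.4 × 7 / √(80 × 2.44) = 1.20, and the largest bias is 0.221 / 1.20 = 0.18 SE.

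**The case against.** The strongest reply is that the section already names the threat and answers it with independent scoring, random order, blinding to period and an outside assessor on every video. The outside-assessor rule is a minimum: two outside assessors are allowed, and nothing says that an in-region assessor will be used or will recognise anyone. All this is true. It makes the risk conditional, but it does not secure the blinding claimed for the second assessor.

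The bias shown is also small and rests on assumed inputs. If in-region assessors came from both regions and favoured their own hospitals equally, the regional difference would cancel. If region were among the covariates of the exposure analysis, the shift would largely drop out; the protocol plans covariate adjustment without listing the covariates. The analysis will also use registered, not planned, exposure. These points stand, and they are why the point is minor.

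Storing the pre-discussion scores is documentation that an SAP or rater manual may already cover, so its absence here is no fault. Who may score which video, and where the third rater comes from, are different: they bear on the scoring rule that the protocol itself sets out.

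A reader might infer more: that the assessors are in fact unblinded, or that the primary TEAM result is materially biased. The documents do not support either. Recognition would be partial, with four hospitals and about 600 staff per region, and assessors are to be blinded to period. One can reach a false-positive rate of about 36% in a post-only comparison, but only by letting one assessor's score shift by 5 points on every video of one arm, with half of it entering the agreed score. Nothing in the protocol suggests that.

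**Conclusion.** The point holds in a limited form. Blinding to region is claimed for both assessors and secured for one, and settlement by discussion gives the other a route into the agreed TEAM score. Whether this happens depends on an in-region assessor being used and recognising staff or ward.

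The size is unknown. Under the assumptions shown it is about 0 in the pre/post-by-region contrast if the shift is constant over time, and at most 0.375 points (0.13 SE) there if it is confined to the post-intervention videos. It is 0.07 to 0.32 points, at most 0.22 SE, in the secondary exposure analysis. These figures illustrate and do not bound the bias.

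Minor severity: a cheap improvement to the scoring rule of a judgement-rated primary outcome, with no reason to doubt the design as a whole.

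**What to change.** - Do not assign an in-region assessor to videos from their own hospital.
- Take any third rater from outside both regions, blinded to arm and period.
- Add a sensitivity analysis of the TEAM score and time to recognition on the outside assessor's independent, pre-discussion score, reported beside the consensus score and also in the exposure analysis. This means keeping the individual scores, which the independent evaluation produces anyway.
- Say in the text that blinding to region is secured for the outside assessor only.

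Consensus after discussion stays the primary scoring rule, and no sample size changes.

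The cost is some constraint on assigning videos, a little more data handling, and a noisier single-rater score in the sensitivity analysis. The RESEARCH PLAN section says post-intervention recording was still under way at this version. The document does not say whether scoring had begun; the assignment rules are best set before it does.

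### The 62 recordings give 80% power for a single two-group comparison; the stated pre/post-by-region primary analysis has about 38% at the planned 32/10/40/40 recordings

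*Protocol*

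**What the plan says.** All the relevant text is in the protocol.

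- **Primary analysis (Statistics):** "Primary analyses will compare pre- and post-intervention data between intervention and control regions". The sentence after it confines the secondary analyses to post-intervention measures, related to training exposure whatever the region.
- **Model and test level (Statistics):** "We will fit Linear regression models to adjust for important covariates"; "A two-sided p-value < 0.05 will be considered statistically significant". No covariates are named and no explained variance is given.
- **Sample size (Statistics):** on the TEAM score, "For sub-study 1, a total of 62 recordings would be needed to show an improvement in the overall TEAM score of 5 points" (SD 7, power 80%). On time to detection, "For sub-study 2, a total of 62 recordings would be needed to show an improvement in time to detection of cardiac arrest of 10 seconds" (SD 14, power 80%). The paragraph does not say which groups or periods are compared.
- **Recordings (Data collection):** "Pre-intervention simulations count 32 in the intervention region and 10 in the control region", then an expected 40 per region after the intervention, 122 in all.
- **Status (Research plan and feasibility):** the PhD student "has successfully conducted the collection of the pre-intervention video recordings". Post-intervention recording is under way, with an "expected total of 120 videos of SBTT from both regions".

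**The concern.** A difference between two changes is estimated less precisely than a difference between two means, because four cell means add their variances instead of two. A sample size derived for two groups therefore does not carry over to the region-by-period contrast. Here the shortfall is made worse by a control pre-intervention cell of only 10.

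The planned total of 122 is almost twice 62, so the study looks comfortably powered. If the primary contrast is in fact more likely to miss the target effect than to find it, a non-significant result could be reported as absence of effect in a study powered at 80%. Because the contrast is not tied to the sample size, there is also room to present as primary whichever comparison turns out significant.

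**Working it through.** **Inputs.** Effects and SDs of 5 points and 7 points (TEAM), and 10 s and 14 s (time to detection), with 80% power and two-sided 0.05, from Statistics. Cell sizes of 32, 10, 40 and 40 from Data collection. Both outcomes have the same standardised effect, d = 5/7 = 10/14 = 0.714, so one calculation serves both.

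**1. Reproducing the 62.** For two independent groups, normal approximation:

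n per group = 2 × (1.960 + 0.842)² / 0.714² = 30.8, rounded up to 31; total 62.

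This is an exact match. The t-test version gives 32 per group (64 in total) and a one-sided test gives 50 in total. So the 62 is the size for one two-group comparison.

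**2. Standard error of the region-by-period contrast.** For four independent cell means with a common SD:

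SE = SD × √(1/32 + 1/10 + 1/40 + 1/40) = SD × √0.18125 = SD × 0.4257

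- TEAM: 7 × 0.4257 = 2.98 points
- Time to detection: 14 × 0.4257 = 5.96 s

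Shares of the variance: intervention pre 17%, control pre 0.10/0.18125 = 55%, each post-intervention cell 14%.

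**3. Power.** Noncentrality = 5/2.98 = 10/5.96 = 1.68. With the noncentral t on 122 − 4 = 118 df, power is 38.4% (38.9% by normal approximation). The effect detectable with 80% power is about 8.4 points or 16.8 s. The expected 95% CI half-width is 5.9 points or 11.8 s. That half-width exceeds the target effects, which restates that power is below 50% and is not separate evidence.

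**4. Does anything rescue the 80%?** The covariate and clustering rows use assumed values, because the protocol gives none.

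| Variation | Power |
|---|---|
| 120 recordings, taken as 32/10/39/39 | 38.1% |
| Unlimited post-intervention recordings, SE factor √(1/32 + 1/10) = 0.362 | about 50% |
| Covariates explain 25% of outcome variance | 48% |
| Covariates explain 50% | 65% |
| Covariates explain 65% | 80% |
| Correlation within hospital and period 0.01 to 0.05, four hospitals per region, 118 df | 37% to 32% |

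To reach 80% with no covariate gain (normal approximation), the contrast would need about 248 recordings in four equal cells, or about 340 at the planned allocation.

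**5. Simpler comparisons.** Post-intervention only, 40 v 40: 88%. Pre v post within the intervention region, 32 v 40: 84%. Both exceed 80%, but neither uses both periods and both regions.

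**Not calculated.** The 64 recordings for longest compression pause cannot be checked, since no SD or baseline is given for the 30% improvement.

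**The case against.** The strongest reply is that the four-cell contrast is inferred. The protocol does not use the words interaction or difference in change, and it speaks of analyses in the plural. The sentence could cover separate between-region comparisons, or a post-intervention comparison with some adjustment for baseline. The small control pre-intervention sample is deliberate, to limit training and Hawthorne effects, and the 80 post-intervention recordings exceed 62. On that view the 62 belongs to a simple comparison with 84% to 88% power, and its arithmetic is correct.

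Part of this stands. The 62 is correctly calculated, and the 38% is conditional on the region-by-period reading. But the sentence names both periods and both regions, and the next one refers to post-intervention measures alone when that is what is meant. A post-only or single-region comparison would leave the 10 control pre-intervention recordings unused. The design is non-randomised, so a contrast that removes baseline differences between regions is the natural primary one. If a simpler comparison was intended, the paragraph still has to say so.

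The clustering range also depends on the model. It falls to 33% to 29% on about 12 df (16 hospital-periods less 4). It rises to 39% to 40% if hospital effects persist across periods and are modelled. None of these approaches 80%.

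A separate analysis plan may specify the model, but the primary comparison, the sample size and the power claim are all stated in the protocol and do not fit together there.

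**Conclusion.** The concern holds. For the TEAM score and time to detection, the protocol's 80% power is not delivered by the analysis it names as primary. Power for 5 points or 10 s is about 38%. This assumes that those effects are the between-region difference in change, that the protocol's SDs apply in all four cells, that recordings are independent, that covariates bring no gain, and that the test is two-sided at 0.05. Covariates would have to explain about 65% of the outcome variance to restore 80%, and the protocol offers no basis for that. Because pre-intervention collection is finished, more post-intervention recordings could lift power to only about 50%. This must be corrected before analysis. No power figure is asserted for the longest pause.

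**What to change.** Restate the sample-size paragraph for the TEAM score and time to detection on the contrast that is primary. Suggested wording:

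> With 32/10/40/40 recordings, assuming independent recordings, equal SDs (7 points; 14 s), no covariate gain and two-sided 0.05, the region-by-period contrast has about 38% power for 5 points or 10 s and 80% power for about 8.4 points or 16.8 s.

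Then name the single region-by-period interaction estimate, with its 95% CI, as the primary result for each of these outcomes. If the 62 was meant for the post-intervention comparison of 40 v 40 (about 88% power), say so explicitly and do not attach it to the pre/post-by-region analysis. For the longest pause, the sponsor should redo the calculation on the same four-cell basis from its own SD and baseline.

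The cost is protocol wording and a less favourable stated power. No further recordings are needed.

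### The 62 recordings are sized for a two-group comparison of independent recordings; the stated pre/post-by-region contrast has about 38% power, and neither the calculation nor the named analyses allow for hospital

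*Protocol*

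**What the plan says.** All of the following is in the protocol's Materials and Methods.

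- **Sample size (Statistics), TEAM score.** "For sub-study 1, a total of 62 recordings would be needed to show an improvement in the overall TEAM score of 5 points". The stated power is 80% and the SD is 7.
- **Sample size (Statistics), time to detection.** The gain sought is 10 s, the SD is 14 and the power is again 80%: "For sub-study 2, a total of 62 recordings would be needed to show an improvement in time to detection of cardiac arrest". Neither statement mentions an ICC, a design effect or hospital.
- **Primary analysis (Statistics).** "Primary analyses will compare pre- and post-intervention data between intervention and control regions".
- **Methods named (Statistics).** "Data will be analyzed using appropriate parametric and non-parametric tests", and "We will fit Linear regression models to adjust for important covariates". The covariates are not listed.
- **Secondary analysis (Statistics).** "Secondary analyses will compare post-intervention outcome measures for each sub-study". The comparison is by how much training the team had received, whatever its region.
- **Recordings (Data collection).** 32 before the intervention in the intervention region and 10 in the control region, then 40 expected in each region afterwards: 122 in total, made in all hospitals.
- **Hospitals (Design, Intervention).** "Both regions include a university hospital and three regional hospitals", so there are eight hospitals, four per region. On who plans the training: "A local investigator in each pediatric department will be responsible for planning the SBTT sessions".

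**The concern.** Two things in the sample-size paragraph do not fit the rest of the plan.

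First, it sizes a simple difference between two groups, while the primary analysis is a difference between two changes. That contrast has four cells, and one of them holds only 10 recordings. A reader who sees 62 needed and 122 planned would think the study amply powered for its primary question.

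Second, recordings from one hospital share a department, its staff and its call routines, and training is planned department by department. Both the level of performance and its change over the year may therefore differ by hospital. A calculation that treats recordings as independent overstates power if they do, and an analysis without a suitable hospital term can give p-values that are too small. At stake are an inconclusive result after a design described as having 80% power, and, under some conditions, a false positive rate above the stated 5%.

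**Working it through.** **Inputs from the protocol.** Two-sided 5%; power 80%; 5 points with SD 7, and 10 s with SD 14 (both d = 0.714 SD); recordings 32, 10, 40 and 40; four hospitals per region. **Assumed:** the ICC (0.01 to 0.10) and the spread of recordings over hospitals, because only regional totals are given.

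**1. The protocol's figure.** n per group = 2 × (1.960 + 0.842)² / 0.714² = 30.8, so 31 per group and 62 in total. This reproduces the stated number for both sub-studies and leaves no margin for clustering.

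**2. The stated primary contrast, independent recordings.**
- Variance in SD² units: 1/32 + 1/10 + 1/40 + 1/40 = 0.181; SE = 0.426 SD.
- For comparison, 31 v 31 gives 2/31 = 0.065, so the real contrast has about 2.8 times the variance assumed. The 10 control pre-recordings alone contribute 0.100 of the 0.181.
- Power at d = 0.714: 0.714/0.426 = 1.678; Φ(1.678 − 1.960) = 38.9%, or 38.4% with a t distribution on 118 df.
- Detectable with 80% power: 2.802 × 0.426 = 1.193 SD, that is 8.3 points or 16.7 s (normal approximation).

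No ICC enters this step.

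**3. Power of the two-group comparison if hospitals differ.** Design effect = 1 + (m − 1) × ICC, with m = 62/8 = 7.75 or m = 80/8 = 10. The power is a normal approximation, before any allowance for having only eight hospitals.

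| Assumed ICC | Design effect, 62 | Power, 62 | Design effect, 80 | Power, 80 |
|---|---|---|---|---|
| 0.01 | 1.07 | 78% | 1.09 | 86% |
| 0.02 | 1.14 | 75% | 1.18 | 84% |
| 0.05 | 1.34 | 68% | 1.45 | 76% |
| 0.10 | 1.68 | 58% | 1.90 | 64% |

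The 80 post recordings keep 80% power while 1 + 9 × ICC does not exceed 80/62, that is up to an ICC of (80/62 − 1)/9 = 0.032.

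**4. Type I error of ordinary regression on the primary contrast.** Simulation of 122 recordings, 20,000 runs per scenario, nominal 5%. Two layouts were assumed. Even: pre 8,8,8,8 and 3,3,2,2; post 10 per hospital. Uneven: pre 14,6,6,6 and 4,2,2,2; post 19,7,7,7 per region. Ranges span both layouts.

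| Hospital variation | ICC 0.01–0.02 | ICC 0.05–0.10 |
|---|---|---|
| Stable over time | 4.8–5.1% | 4.2–4.7% |
| Half stable, half period-specific | 5.1–5.8% | 6.2–8.3% |
| Entirely period-specific | 5.8–6.5% | 7.8–12.0% |

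Adding hospital as a plain covariate does not help in the last row (5.8–6.5% and 8.0–12.5%), because it removes stable differences but not hospital-specific change. A comparison of hospital-level changes (post mean minus pre mean, 4 v 4 hospitals, 6 df) held about 5% throughout (4.8–5.5%), with 21–33% power at d = 0.714.

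**The case against.** The strongest reply has four parts.

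- **The model belongs in the analysis plan.** The protocol gives an outline, its covariates are open, and hospital could be among them. This stands in part: one can say only that no named analysis mentions hospital, not that hospital will be ignored. It does not rescue the sample-size paragraph, which is fixed in the protocol and does not match the protocol's own primary analysis.
- **The stated primary contrast is largely cleared.** With stable hospital differences the test is nominal or slightly conservative, and at ICC 0.01–0.02 it is near nominal in every scenario. This stands. Clear inflation needs both an ICC of 0.05–0.10 and hospitals that drift differently, and the protocol documents neither.
- **80 post recordings already exceed 62.** True, but only for a post-only comparison and only up to an ICC of about 0.03. It does not apply to the pre/post contrast.
- **The shortfall in power is not a clustering problem.** Correct. The 38% holds with no clustering at all, and the two parts should be read separately. The protocol also gives a reason for the small control pre-sample (avoiding training and Hawthorne effects), but the calculation does not reflect its cost.

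Stronger readings go beyond the document. A reader might infer a false positive rate of 15–19%; that arises at ICC 0.10 in a post-only comparison of regions, which the protocol does not name as its primary analysis. A reader might infer that some 248 recordings are required at ICC 0.10. With eight hospitals fixed, N = 62 × 0.90 / (1 − 62 × 0.10/8) = 248, but the denominator is only 0.225, and starting from the unrounded sample size gives about 240, so the figure is too fragile to write into a plan. Nor can an error rate be attached to the training-exposure analysis: it depends on how exposure varies within hospitals, which the protocol does not report. Having one region per arm is a limitation of an openly non-randomized design, not an error in the calculation.

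**Conclusion.** The point holds in two parts of different strength.

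**Firm:** the 62 for sub-studies 1 and 2 belongs to a two-group comparison of independent recordings. The stated primary contrast has about 38% power at 5 points or 10 s, not 80%. This rests only on the protocol's own counts, effects and SDs, and on reading the primary analysis as the difference between regions in pre-to-post change.

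**Conditional:** neither the calculation nor any named analysis allows for hospital. Its size rests on an assumed ICC and an assumed spread of recordings over hospitals. At ICC 0.01–0.10, a two-group comparison of 62 recordings loses between about 2 and 22 percentage points of power from 80%. The primary test is too liberal to a degree that matters only with hospital-specific change at the upper end of that range.

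This should be fixed. Confidence is high for the first part and moderate for the second. Sub-study 3 (64 recordings) is not covered, because no SD is given for it.

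**What to change.** 1. **Sample-size paragraph.** State that 62 refers to a two-group comparison of independent recordings. Add that the pre/post-by-region contrast with 32, 10, 40 and 40 recordings has about 38% power at 5 points (SD 7) or 10 s (SD 14), that 80% power is reached at about 8.3 points or 16.7 s, and that an analysis allowing for hospitals that change differently will have less. Give the loss from clustering as a range over assumed ICCs, as in the table above, not as one required total.
2. **Primary analysis.** Account for hospital with a method that allows hospital-specific change. Two options are a comparison of hospital-level changes between regions (4 v 4, 6 df), or a mixed model with hospital and hospital-by-period effects and a small-sample correction. Transform durations where needed. The first is the simpler and held its level in simulation. In the second, at least one variance component was estimated at zero in 64–93% of simulated fits, so it should not stand without a check.
3. **Training-exposure analysis.** Include a hospital term.

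Cost: wording only. The Research plan section says post recordings were still being made, and the hospital of each recording is known, so no new data or recruitment are needed. The price is wider intervals and a less favourable stated power: about 21–33% for the hospital-level comparison at the protocol's effect, against 38% nominally for ordinary regression.
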